1. STUDY OVERVIEW, PURPOSE, AND BACKGROUND

1.1. Significance of Distress among lesbian, gay, and bisexual (LGBT) cancer survivors

To date, LGBT survivors have been invisible in the cancer control literature.^{1,2} Epidemiological studies of cancer prevalence often do not assess sexual orientation,² and even studies of the needs of diverse populations of cancer patients and survivors have remained mute on the subject of sexual orientation.³⁻⁵ The few studies that have focused on LGBT cancer issues have found that subgroups of LGBT persons are up to 2.1 times more likely to be diagnosed with cancer than their heterosexual counterparts,^{6,7} and that physical and mental health disparities impact LGBT cancer survivors.⁷⁻⁹ Distress, a negative psychological reaction to the cancer experience, is among the most common side effects cited by survivors of any sexuality,^{10,11} is 1.7 times more common among LGBT survivors,¹² and is linked to increased morbidity¹³ and mortality.¹⁴ Lesbian survivors report poorer quality of life⁸ and more anxiety and depression post-diagnosis than heterosexual women,⁹ while gay male survivors report worse mental health and more fear of cancer recurrence than heterosexual men.^{15,16} Given the large number of LGBT survivors (between 420,000-1,000,000 living in the United States^{17,18}), higher rates of distress among these survivors, and the link between distress, morbidity, and mortality, interventions targeting distress among LGBT cancer survivors are urgently needed. There is also a need for interventions that are socioculturally tailored to the needs of this population.^{19,20} Targeting psychological distress in LGBT survivors through a partner-assisted intervention could reduce the public health burden of long-term cancer survivorship by reducing chronic distress and morbidity among survivors²¹⁻²³ and promoting intervention adherence.²²⁻³⁰

1.2. Exercise as intervention to reduce distress

Receiving a diagnosis of cancer can cause psychological distress.³¹ Distress among LGBT cancer survivors is further exacerbated by LGBT-specific stressors, such as discrimination based on sexual orientation and invisibility/non-recognition of caregivers.^{1,32} Exercise, including walking and resistance training, is safe and well-tolerated and improves distress in heterosexual cancer survivors.³³⁻³⁶ Our intervention, EXCAP® (Exercise for Cancer Patients), is a standardized, daily, 6 week, home-based, progressive exercise program. In phase II randomized controlled trials (RCTs) of this program, survivors (N = 91) who completed EXCAP® demonstrated improvements in distress, quality of life, and markers of inflammation.^{33,37,38} Adherence to the intervention was good (79% completion rate), and there were no adverse events.³³⁻³⁶ As EXCAP® is a standardized exercise program, it is easy to prescribe and tailor to survivors; it is home-based, exportable, and may be more palatable than weekly psychotherapy.^{39,40}

1.3. Support, distress, and exercise

[figure not shown]
In our formative research, LGBT survivors reported feeling less distressed when their caregivers were included in cancer care visits.⁴¹ We have also shown that partner support is directly linked to reductions in LGBT-specific stress among LGBT adults.^{12,42,43} In tailoring an intervention for LGBT survivors, it is critical to welcome support from caregivers in order to reduce LGBT-specific stress. Also, two RCTs have shown that exercise interventions incorporating support from a caregiver may increase adherence and produce significant improvements in clinical outcomes among cancer survivors.^{44,45} In the first, survivors who exercised with a

Protocol date: 7/06/2020

caregiver were more adherent to the intervention than those who did not.⁴⁵ In the second, survivors and caregivers receiving an exercise intervention as a dyad reported less distress.⁴⁴ However, neither study compared the efficacy of a partner-assisted exercise intervention to a survivor-only intervention, nor were LGBT survivors recruited. Thus, while preliminary evidence indicates that including caregivers in exercise interventions may be effective, no RCTs have evaluated the efficacy of a partner-assisted exercise intervention in reducing psychological distress among LGBT cancer survivors.²¹⁻²³

1.4 Integrated biopsychosocial model of the impact of exercise on distress: Cancer influences psychological distress on several levels. First, receiving a diagnosis of cancer can produce symptoms of depression and

Model A: Traditional exercise (EXCAP®) for LGBT cancer survivors

Model B: Novel exercise with partner assistance (EXCAP-PA) for LGBT cancer survivors

[figure not shown]

Figure 2: Biopsychosocial model of dyadic intervention

anxiety.^{31,46} This distress has been shown to negatively impact both cancer survivors and their caregivers,^{2,45-49} reduce the provision of social support within the survivor/caregiver dyad,¹⁰⁻¹¹ and consequently increase psychological distress. Cancer and treatment also impact stress processes⁴⁷ and increase activation of

markers of inflammation.⁴⁸ Increased activation of the HPA axis and concomitant increases in systemic inflammation can result in increased report of psychological distress.⁴⁹⁻⁵¹ In previous studies, cortisol, C-reactive protein, and serum amyloid A are particularly linked to report of distress.⁵²⁻⁵⁷

Therefore, EXCAP® is designed to reduce distress on two levels. On a psychological level, participation in exercise serves as a form of behavioral activation and increases self-efficacy, factors that have been shown to reduce distress.²²⁻³⁰ On a physiological level, exercise affects biological processes associated with the stress response, as measured by reduction in levels of distress-related biological endpoints (Figure 2).³⁷ This study will test direct effects of exercise on reduction in psychological distress and these biological endpoints. Previous research on this model by our group has shown that exercise does improve distress and that changes in immune function significantly predict changes in distress ($p < 0.05$, $r = 0.12$).³⁸

[figure not shown]
Including a caregiver in an exercise intervention, similarly, could affect distress on a psychological level by increasing perception of social support,⁵⁸ and on a physiological level by increasing intervention adherence.⁴⁵

1.5 Preliminary data

The preliminary data presented illustrates four key points: 1) Disparities exist among LGBT cancer survivors;

Protocol date: 7/06/2020

Figure 3: Z-scores comparing LGBT (N=293) and heterosexual (N=5,386) cancer survivors (all cancer types)

2) LGBT survivors and their partners want specific interventions, 3) EXCAP[®] is effective in reducing distress, and 4) recruiting and retaining LGBT cancer survivors and caregivers is feasible.

Study 1) Distress is prevalent among LGBT

cancer survivors: In secondary data analyses of large datasets (BRFSS, LIVESTRONG), we found that LGBT cancer survivors reported 2.96 more days per month of poor mental health (p=0.02), 60 fewer minutes of physical activity per week (p=0.01), and 1.9 times greater odds of difficulty with social support (p=0.04) than their heterosexual counterparts.¹² (See Figure 3.)

Study 2) LGBT cancer survivors and their

partners want specific interventions: In a focus group conducted with 10 lesbian and gay cancer survivors and their caregivers, we ([name], with consultation from mentors) found that **both** cancer survivors **and** their partners experience psychological distress, including concerns about the impact of treatment on their relationship and about cancer recurrence. Multiple dyads reported that this distress directly affected their relationship with one another and that few resources are available for cancer survivors in the LGBT community. **All** LGBT survivors and their caregivers we spoke with indicated that they would be interested in a tailored exercise intervention.

Study 3) The EXCAP intervention is effective in reducing distress: In a secondary analysis of [name] study of EXCAP[®] for prostate cancer survivors (n=58), we found that EXCAP[®] significantly reduced distress as measured by the POMS Total score. Compared with usual care control, 6 weeks of EXCAP[®] was associated with a 7.24 point reduction in the POMS Total score (p = 0.02; manuscript under review).³⁸ This secondary analysis also included evaluation of immune function; while markers of HPA axis function and early inflammation were not included in this dataset, preliminary analysis of immune function piqued my interest in exploring this biological mechanism further.

Study 4) It is feasible to recruit and retain LGBT cancer survivors and their partners in an exercise intervention:

[name] was recently (2013) awarded a seed grant to conduct a feasibility study, entitled "Dyadic Exercise Intervention for Heterosexual and LGBT Cancer Survivors and Their Caregivers." This study, conducted with the input of the mentorship team, was designed to assess the **feasibility and acceptability** of delivering an exercise intervention to heterosexual and LGBT dyads, as well as establishing **preliminary efficacy of the same outcome measures to be used in the proposed Phase II RCT**. We developed a novel, dyadic delivery method for EXCAP[®] (EXCAP-PA; see Appendix), involving training caregivers to support survivors in exercising, as well as new LGBT recruitment and retention methodologies. We have recruited and retained 20 LGBT survivors and their diverse caregivers, successfully delivered the intervention, and had good adherence and acceptance. We also built strong community collaborations and partnerships.

2. HYPOTHESIS AND AIMS

2.1. Overall Hypothesis

The overall hypothesis of this study is that among LGBT survivors, EXCAP-PA, incorporating caregiver support, will be more efficacious than survivor-only EXCAP[®] in improving biopsychosocial aspects of distress: both self-reported psychological distress and biological endpoints associated with distress. Exploratory hypotheses are that improvement in distress, increased social support from the caregiver, and intervention adherence will be positively related, and that caregivers will also benefit from partner-assisted intervention.

2.2 Primary Aim (in survivors)

- 2.2.1 To determine the preliminary effect of EXCAP-PA versus survivor-only EXCAP[®] on self-reported psychological distress (Profile of Mood States [POMS] total score).

2.3 Secondary Aims (in survivors)

- 2.3.1 To determine the preliminary effect of EXCAP-PA versus survivor-only EXCAP[®] on biological endpoints associated with distress: markers of HPA axis functioning (cortisol) and markers of early inflammation (serum amyloid A [SAA], C-reactive protein [CRP])
- 2.3.2. To determine the preliminary effect of EXCAP-PA versus survivor-only EXCAP[®] on social support from the caregiver (Dyadic Support Questionnaire [DSQ]) and intervention adherence (actigraphy).

2.4 Exploratory Aims (in survivors):

- 2.4.1 To explore preliminary mechanistic relationships between self-reported distress, markers of HPA axis functioning and early inflammation, social support from the caregiver, and intervention adherence.

2.5 Exploratory Aims (in caregivers):

- 2.5.1 To determine the preliminary effect of EXCAP-PA versus survivor-only EXCAP[®] on self-reported psychological distress and biological endpoints associated with distress among caregivers.

3. CHARACTERISTICS OF THE RESEARCH POPULATION

Targeted/Planned Enrollment Table

Total Planned Enrollment: 140

TARGETED/PLANNED ENROLLMENT: Number of Participants			
Ethnic Category	Sex/Gender		
	Females	Males	Total
Hispanic or Latino	7	7	14
Not Hispanic or Latino	63	63	126
Ethnic Category: Total of All Participants	70	70	140
Racial Categories			
American Indian/Alaska Native	0	0	0
Asian	2	2	4
Native Hawaiian or Other Pacific Islander	0	0	0
Black or African American	10	10	20
White	58	58	116
Racial Categories: Total of All Participants	70	70	140

3.1 Subject Characteristics and Number of Participants

Participants in this randomized controlled trial will be 70 LGBT cancer survivors and their 70 caregivers (a total of 70 dyads/140 individuals). A caregiver is defined as any individual whom the cancer survivor nominates as having provided emotional support or tangible assistance without pay during the survivor's cancer experience. No restriction will be placed on caregivers in terms of relationship with the cancer survivor; they can be family members, friends, romantic partners, or community members.

3.2 Gender, Age, and Racial/Ethnic Origin of Participants

Based on the characteristics of samples recruited for previous exercise studies run out of the **Physical Exercise Activity Kinesiology Laboratory (PEAK Lab)** at the University of Rochester, we anticipate that the sample for the current study will be 49% male and 51% female. Average age will be 67 years. The ethnic composition of the sample will be approximately 92% White/Caucasian, 15% African-American, and 3% Asian; 10% will

Protocol date: 7/06/2020

report a Hispanic/Latino ethnicity. Children, as defined by the National Institutes of Health Grants Policy Statement, will not be included, as cancer survivors under 21 years of age are often considered to fall under pediatric care, and may have a very different experience of cancer and caregiving than adult (age 21+) cancer survivors.

3.3 Inclusion Criteria (Survivors): To be included in the study, cancer survivors must:

- 3.3.1 Have had a diagnosis of cancer (any cancer type excluding squamous and basal cell [skin cancers]) and have completed primary surgery, chemotherapy, and/or radiation therapy (those on continued, indefinite adjuvant treatment are still eligible),
- 3.3.2 Identify as lesbian, gay, bisexual, or transgender, or have a same-sex romantic partner,
- 3.3.3 Have a caregiver willing to participate in the study (defined as anyone who provided emotional support or tangible assistance during the survivors' cancer experience),
- 3.3.4 Be able to read English,
- 3.3.5 Be 21 years of age or older, and
- 3.3.6 Give written informed consent or electronic consent.

3.4 Inclusion Criteria (Caregivers): Caregivers must:

- 3.4.4 Be nominated by a cancer survivor,
- 3.4.5 Be able to read English,
- 3.4.6 Be 21 years of age or older,
- 3.4.7 Give written informed consent or electronic consent.

3.5 Exclusion Criteria: Participants must not:

- 3.5.4 Have physical limitations (e.g., cardiorespiratory, orthopedic) contraindicating participating in a low- to moderate-intensity home-based walking and progressive resistance program and physical function testing, as assessed by their medical oncologist, their primary care physician, and/or the study medical monitor (or any of these three physicians' designees),
- 3.5.5 For caregivers, be currently undergoing active treatment for cancer.

4. PARTICIPANT IDENTIFICATION, RECRUITMENT AND CONSENT

4.1 Human Subjects Involvement: The proposed RCT aims to recruit 70 lesbian, gay, bisexual, and transgender (LGBT) cancer survivors who have completed treatment (surgery, radiation, or chemotherapy) or who are on continued, indefinite adjuvant treatment, so as to have a final, evaluable sample of 60 LGBT survivors after attrition. The proposed RCT will also recruit caregivers (broadly defined) of the above cancer survivors. Each recruited cancer survivor will be asked to name a person who they feel provided care (emotional, informational, tangible, etc.) during their cancer experience, with no further strictures placed on this relationship in terms of type or duration. The caregiver will be approached to participate in the RCT. Thus the sample will consist of 70 LGBT survivors (60 evaluable) and their caregivers (140 individuals total/120 evaluable). Recruitment and primary analyses will specifically target the LGBT cancer survivor.

LGBT survivors will be randomized to one of 2 arms: Arm 1, a novel, *partner-assisted*, LGBT-specific framework incorporating EXCAP[®] (Exercise for Cancer Patients, a standardized, daily, 6 week, progressive walking and resistance training program), in which both survivors and caregivers will receive EXCAP[®] materials and be instructed in their use together, or Arm 2, a *survivor-only* version of EXCAP[®], in which only the cancer survivor will receive EXCAP[®] materials and be instructed in their use. There will be 35 LGBT survivors randomized to each arm (30 evaluable), along with their 35 caregivers (30 evaluable). Survivors and caregivers will be assessed before and after the 6 week intervention in both arms. The LGBT survivor will be the primary unit of analysis; data collected from caregivers will be used for exploratory purposes only.

Assuming an 85% retention rate and an initial sample of 70 survivors, 60 LGBT survivors will complete the study. Because LGBT survivors are the primary unit of analysis, survivors will be invited to return for follow-up assessment even if their caregivers are unavailable. Study interventions will begin on Study Day 0 and continue for 6 weeks (42 days). The exercise intervention, EXCAP[®], is a standardized intervention developed and tested by the research team at University of Rochester Medical Center (URMC). The actual list of exercises, and the framework for the partner-assisted EXCAP-PA, is provided in the Appendix. Each participant will be monitored by an American College of Sports Medicine Certified Exercise PhysiologistSM. Assessments will be made with validated and methodologically sound measures including self-report questionnaires, assays for expression of biological endpoints, weekly diaries, and actigraphy monitoring.

No special classes of participants such as fetuses, neonates, pregnant women, prisoners, institutionalized individuals or other vulnerable populations will be recruited.

Children, as defined by the National Institutes of Health Grants Policy Statement, will not be included, as cancer survivors under 21 years of age are often considered to fall under pediatric care and may have a very different experience of cancer treatment and caregiving than adult (age 21+) cancer survivors.

All data will be gathered at the PEAK Lab and the URMC Cancer Control Unit.

4.2 Method of Participant Identification and Recruitment

Protocol date: 7/06/2020

4.2.1 LGBT Survivor Recruitment: All data will be gathered from participants 21 years of age or older. Participants are cancer survivors who have completed treatments or caregivers of cancer survivors; both survivors and caregivers are able to read and understand English. Potentially eligible cancer survivors will be contacted through several channels.

1) Distal identification of URM patients: First, the study team will monitor URM patients over the age of 21 who have been diagnosed with cancer (any site), who have completed cancer treatment or are on indefinite treatment, and who are LGBT identified or same-sex partnered. This monitoring will be done through e-record as well as with TriNetX, a clinical query tool that allows researchers to pull specific subject criteria from e-record. Search criteria for TriNetX will include “malignant neoplasm” as well as other specific cancer diagnoses, report of being “partnered” or having a “same-sex partner” on sociodemographic questions, or identifying as lesbian, gay, bisexual, or transgender. Use of TriNetX software requires an RSRB approved protocol; any data from this service is transferred to the study team via a secure web-based interface. If an LGBT cancer survivor identified via TriNetX is deemed eligible after a review of their medical record, the study team will contact the survivors’ physician to ensure eligibility and will then send the survivor a letter, from their physician and the study team, explaining the study and its requirements. A brochure providing further details will also be enclosed (see Recruitment Materials). Survivors will have the option to opt out of further contact; if the survivor is willing to continue, a study team member will make contact to conduct screening.

2) Direct referral of URM patients: Second, study staff work with physicians, nurses, and other care providers in URM clinics to identify patients who have been diagnosed with cancer (any site), who have completed cancer treatment or are on indefinite treatment, and who have identified themselves as LGBT or same-sex partnered to their care providers. After being referred by their care provider and deemed eligible following a review of their medical record, survivors will be sent a letter from their physician and the study team, explaining the study and its requirements. Study team members will also be present in the URM clinics of affiliated care providers so that cancer survivors who are scheduled for appointments and who might be eligible can be referred by their treatment team to the study. Following the referral by the treatment team, the treatment team will introduce the study team member, who will meet with the survivor and explain the study either in person or over the phone. If a caregiver has accompanied the survivor to the clinic, they will be informed about the study at the same time, either in person or via phone. If the survivor (and caregiver) is willing to continue, a study team member will conduct screening. Letters and brochures describing the study will be sent to the homes of survivors and caregivers contacted at the clinic.

3) Community recruitment and referral: We will also advertise the study on the University of Rochester Medical Center “Clinical Trials” website, in local newspapers, through flyers posted in the community, and through the PEAK Lab Facebook page. To ensure recruitment of LGBT cancer survivors, we will also recruit through community groups, such as those hosted by the Out Alliance of the Genesee Valley and through providers at Trillium Health, who specifically provide services to the LGBT community; we will leave brochures and tear-off posters at both locations and present the study to staff at both locations. We will recruit through newspaper

advertisements; through website postings targeting the LGBT community; and through word-of-mouth, referrals, and snowball recruitment within the LGBT community.

Snowball recruitment methods will involve asking recruited participants to pass information about the study on to other interested LGBT cancer survivors and/or their caregivers. Due to the stigmatized nature of LGBT identities and cancer diagnoses, steps will be taken to ensure that recruited participants do not feel unduly coerced to participate in snowball recruitment and that the confidentiality of other LGBT cancer survivors in the community is maintained. We will include verbiage in the consent form whereby recruited participants can indicate whether they are willing to contact other LGBT community members about the study. Those who consent to contact other LGBT community members will be provided with RSRB approved brochures to give to potentially eligible community members. Research staff will follow up with these participants while study recruitment is ongoing to see if they need additional brochures; if so, additional brochures will be mailed to participants' home addresses.

Interested potential participants who contact the study through any of these means will be mailed a letter and brochure and screened via phone by a member of the study team.

4.2.2 Caregiver Recruitment: A similar procedure will be followed for the caregiver; after being nominated by a survivor, the caregiver will be told about the study immediately (if the caregiver is present at a clinic visit or with the cancer survivor during telephone contact), or sent a letter from the study team explaining the study and providing the option to opt out of future contact. If the caregiver is willing to continue, the study team member will conduct screening.

4.3 Screening: After a member of the treatment team has referred the potential participant, or the potential participant has contacted the research team, screening of potential study participants will be conducted either in person or over the phone by research staff trained to explain the project, recruit, and screen participants (see Telephone Script). Verbal consent to conduct this screening will be obtained using the telephone script. Screening will focus on the cancer survivor's eligibility, with caregivers nominated by survivors. Individually identifiable information will not be kept on potential participants who decline to participate in the study, though we will note gender and race/ethnicity for the purpose of monitoring our success in recruiting women and racial/ethnic minorities.

Eligibility of the dyad will primarily be established using cancer survivors' characteristics. After a member of the treatment team has referred the LGBT cancer survivor or the survivor has contacted the research team, the survivor will be screened for eligibility either via telephone or face to face. In both screening approaches, a trained staff member will ask survivors about: (1) cancer diagnosis and treatment, (2) identification as lesbian, gay, bisexual, or transgender, or partnership with a same-sex romantic partner, (3) medical contraindications to exercise, and (4) presence and availability of a primary caregiver.

Following screening of the cancer survivor, a study team member will ask for the survivor to nominate a caregiver. Caregivers will then be screened either via telephone or face-to-face. After the caregiver has been contacted by the study team for screening, or if the caregiver initiates contact with the study team, screening

will focus on assessing willingness to participate and ruling out medical contraindications to engaging in moderate walking and resistance training.

After completing screening of survivors and caregivers, a study team member will schedule survivors and caregivers for an informed consent session at the PEAK Lab, or will offer the option for participants to complete an electronic consent form (e-consent). If consent is obtained in person, caregivers and survivors can attend this session either as a dyad or as individuals; if consent is obtained electronically, caregivers and survivors will be sent individual copies of the e-consent form (see section 4.4 below).

After screening and establishing informed consent, but before the baseline assessment, medical eligibility for participants will be further verified by contacting the survivor's and caregiver's oncologist or primary care physician. With the participants' verbal consent, a study team member will fax a form indicating that the participant has no medical contraindications to participating in a moderate intensity exercise program or physical function assessment (see Appendix). The physician (or designee) will verify and sign this form. The form will be returned to the study team before the baseline assessment meeting. Alternately, the medical monitor will assess the participant to rule out medical contraindications to participating in a moderate intensity exercise program.

After consenting and verification that there are no medical contraindications to participating in an exercise program or physical assessment for either participant, dyads will be scheduled to return to the PEAK Lab for a baseline assessment and randomization to an intervention arm.

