clinical crisis intervention. He has taken continuing education courses specifically focused on the assessment and treatment of domestic violence. In addition, a resource list will be available which will include emergency housing shelters, and programs, clinicians, and support groups specializing in relationship abuse and violence. For more minor relationship disruptions that may result from participation, we will have referral information available for therapists who treat dyads and families.

- 9.2.3 **Confidentiality:** This study involves collecting biological samples and obtaining access to medical records, and steps must be taken to protect both participant data and identity. The following confidentiality protection steps will be taken: 1) Research staff will participate in initial training, follow-up training, and ongoing monitoring and supervision to ensure understanding of the ethical issues involved in this research; 2) only the research staff will know the name, identification (ID) number, and contact information of participants. The list that links the participant's name with ID number will be kept on an encrypted drive accessible only by the research staff; 3) consent forms will be kept in locked filing cabinets in a locked office, again accessible only by research staff; and 4) any personal identifiers linked to data will be removed and replaced by non-identifying ID numbers in all records. The electronic files that contain quantitative data will be stored on a secure University of Rochester Medical Center file server. These files will be password protected and accessible only by the PI and the study coordinator.

Due to the dyadic nature of the proposed study, additional precautions are necessary to avoid inadvertent transfer of confidential information from one partner to another as a result of participation in assessments. Quantitative assessments are conducted separately with each partner so that it is not possible for research staff to reveal information to one partner about the other partner.

- 9.3 ***Benefits:*** There are no direct benefits of the study to the study participants. Potential secondary benefits of the study include that all participants will receive an exercise kit to keep at no charge. Caregivers in the individual intervention group will receive the kit and instructions after completing all of the study assessments. Participants may or may not receive any further benefit from participating in this study.

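### Section 4.2.1 has a caregiver who is present in clinic told about the study alongside the survivor, while 4.2.2 and 6.2.4 require nomination first; the conflict leaves a route by which the survivor's LGBT status could be disclosed

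*Combined protocol and SAP*

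**What the plan says.** Four places in the combined protocol and SAP bear on when a caregiver learns of the study.

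- **Section 4.2.1, channel 2 (direct referral in clinic).** After the treatment team's referral and introduction, a study team member explains the study to the survivor. The text continues: "If a caregiver has accompanied the survivor to the clinic, they will be informed about the study at the same time". It then says: "If the survivor (and caregiver) is willing to continue, a study team member will conduct screening". Letters and brochures later go to the homes of both people contacted at the clinic.
- **Section 4.3 (screening).** Among the survivor's screening questions is "2) identification as lesbian, gay, bisexual, or transgender, or partnership with a same-sex romantic partner". The nomination step comes later: "Following screening of the cancer survivor, a study team member will ask for the survivor to nominate a caregiver".
- **Section 4.2.2 (caregiver recruitment).** For the same clinic situation it says "after being nominated by a survivor, the caregiver will be told about the study immediately (if the caregiver is present at a clinic visit".
- **Section 6.2.4.** It also places nomination before any contact with the caregiver, here by letter.

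Section 3.1 defines a caregiver by the survivor's nomination and leaves the relationship open: "they can be family members, friends, romantic partners, or community members". In the clinic channel, survivors are described as having disclosed their identity to their care providers. Nothing is said about whether the companion knows.

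**The concern.** LGBT identity or a same-sex partner is the condition for entry (3.3.2), so an accurate account of who the study is for tells a listener something about the patient being approached. A survivor who is out to an oncologist need not be out to the relative, friend or community member in the next chair.

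The protocol recognises the sensitivity. It describes LGBT identities as stigmatized when it discusses snowball recruitment (4.2.1), measures concealment as part of minority stress (10.1.8), names loss of confidentiality among its four risks (9.1) and acknowledges possible conflict or violence within a dyad (9.1.3). Disclosure at this stage would come before consent, could reach people who never enrol, and cannot be undone.

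**Working it through.** No arithmetic applies. The plan states no figure on this point, and the question is one of sequence. The check sets the passages side by side.

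1. **Order under 4.2.1 channel 2 with 4.3:** referral and introduction; study explained to survivor and accompanying caregiver together; screening; nomination.
2. **Order under 4.2.2 and 6.2.4:** nomination; caregiver told if present, or sent a letter; caregiver screened.
3. **Can the definition of caregiver reconcile them?** If the caregiver in 4.2.1 means someone already nominated (3.1, and inclusion criterion 3.4.4), nomination must come before the joint explanation. But 4.2.1 puts the explanation before screening, and 4.3 puts screening before nomination. Nomination would then have to come both before and after the explanation, so the definition alone does not resolve the conflict.
4. **Can a looser reading of the timing reconcile them?** The sentence could mean only that both people are told during the same visit. The next step in 4.2.1 counts against this: the caregiver's willingness appears alongside the survivor's before screening is done, so the caregiver has already been told something.
5. **Does another clinic passage settle it?** Section 6.2.3.1 has the care team introduce the study to the survivor, then a description, then screening. It does not mention a companion. No section has the survivor agree, in private, before someone else is told.
6. **Would an explanation be revealing?** Pointing towards yes: the entry criterion (3.3.2); the Arm 1 content on LGBT minority stress (5.2, 6.6.1); and 6.2.5, under which staff explain study details with the consent document as a guide. Section 4.2.1 says that document will ask about willingness to contact other LGBT community members. Pointing the other way: the physician letters in the Appendix carry a neutral title and do not mention LGBT status. The brochure, script and consent form cannot be checked.
7. **Do existing safeguards cover the step?** The steps against stigma in 4.2.1 are written for snowball recruitment. Section 9.2.3 says "additional precautions are necessary to avoid inadvertent transfer of confidential information from one partner to another", but limits this to transfer arising from assessments. Sections 9.2.3 and 4.3 also require staff training and supervision in general terms. None of these sets an order for the clinic approach.

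**The case against.** The strongest reply is that nomination governs throughout. Section 4.2.2 is the section on caregivers and covers the clinic visit expressly; 6.2.4 agrees; 3.1 and 3.4.4 build nomination into what a caregiver is. On this view 4.2.1 is loosely worded, and trained staff would handle it sensibly. Part of this stands: telling people who have not been nominated is not the plan's settled rule. But staff who read 4.2.1 and 4.3 would act differently from staff who read 4.2.2, and general training does not tell them which to follow. Even 4.2.2 has the caregiver told at once, without confirming that this person may learn what the study is about.

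A reader might infer more than the documents support:

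- **That any companion is told.** The text says a caregiver, although it gives staff no means of identifying one before nomination.
- **That survivors are asked about identity in front of the companion.** Section 4.3 does not say that screening is joint; it also does not say that it is private.
- **That the survivor hears nothing beforehand.** Sections 4.2.1 and 6.2.3.1 have the treatment team refer and introduce first.
- **That disclosure is certain.** What a companion would hear depends on materials not supplied.
- **That a rate of disclosure can be given.** The documents give neither the number of accompanied clinic approaches nor the share of survivors who are not out to their companion.

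**Conclusion.** The concern holds as an internal contradiction with a confidentiality consequence. Section 4.2.1 channel 2, read with 4.3, has an accompanying caregiver told before nomination; 4.2.2 and 6.2.4 require the reverse; and no section provides for the survivor's prior private agreement. Following 4.2.1 could disclose that a survivor is LGBT or same-sex partnered.

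The conclusion about disclosure assumes that the spoken explanation conveys the entry criterion or the Arm 1 content. That is likely given 3.3.2 and 6.2.5, but unconfirmed. The size cannot be quantified. The point does not touch the primary endpoint, the power calculation or any planned analysis. It should be corrected because the possible harm is irreversible, falls within a risk the protocol itself names, and is cheap to prevent.

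**What to change.** In 4.2.1 channel 2, replace the sentence on simultaneous information with an order consistent with 4.2.2 and 6.2.4:

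1. The study is explained to the survivor, and the identity question asked, out of the companion's hearing.
2. The survivor nominates a caregiver and confirms that this person may be told the study's focus.
3. Only then is the caregiver informed in person, or mailed the letter and brochure.

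Align 4.2.2, 4.3 and 6.2.4 with this order, including the confirmation in step 2, and check that the telephone script and brochure agree with it.

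The cost is a short amendment and a few minutes of private conversation, with some caregivers told slightly later. No visits, measures or analyses change. The change removes this route of disclosure; it does not guarantee that disclosure cannot happen in another way.
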